### 9.2 COLLECTION AND DERIVATION OF PRIMARY AND SECONDARY OUTCOME MEASURES

All exploratory variables will be analyzed as reported, without further derivation, except for the calculation of change from baseline, or change from prior time-points.

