### 2.2 BACKGROUND AND CLINICAL RATIONALE FOR DATA REVIEW

Trigger finger is an entrapment tendinopathy in which the flexor tendon catches within a thickened or narrowed A1 pulley with flexion and extension of the digit. Patients present with complaints of pain, snapping, or locking of the finger at the MCP joint. With an incidence between 2 and 3% in the general population, trigger finger is one of the most common causes of disability and pain in the hand.

Initial treatment is conservative and nonsurgical management includes: non-steroidal anti-inflammatory drugs, activity modification, splinting, and corticosteroid injections. Though some relief may be noted initially, the reported recurrence rate after corticosteroid treatment is up to 48%. Definitive treatment often requires release of the A1 pulley through an open, percutaneous, or endoscopic surgical technique. In the open approach, an incision is made in the palm - most commonly at the distal palmar crease - which causes great discomfort to patients. The endoscopic approach reported by Pegoli and colleagues requires two incisions: one at the proximal interphalangeal crease and one in the mid palm. The percutaneous approach avoids use of these painful palmar incisions, but concerns exist over the safety of this blind technique. As such, techniques currently available for the surgical treatment of trigger finger fall short in one of two ways: 1) they require an incision of the palm, which can be painful and unsightly to patients or 2) the release is performed blindly.

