#### 4.4 STUDY QUESTIONNAIRES/ASSESSMENT

The patients of [name], [name], [name], and [name] eligible to participate in the study will proceed with baseline assessments once study consents have been signed and the patient has been enrolled in the study.

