#### 6.1.1 PROCEDURES FOR FINAL STUDY ENTRY

A subject is considered "enrolled" when he/she has signed the IRB-approved consent form and HIPAA authorization in the presence of the Investigator, who will then collect and record the subject's demographic information and medical history.

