#### 6.1.2 PRE-OPERATIVE VISITS

The subject will be screened in accordance with the inclusion/exclusion criteria, medical history will be collected, a physical exam will be performed and medical photography will be obtained, as is the standard of care.

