#### 6.1.3 FOLLOW-UP VISITS

Subjects will be required to attend post-operative visits at 1 week, 1 month, and 6 months post-operatively, as is the standard of care. Review of medical history and physical examination will be conducted at all post-operative visits. At 1 week, 1 month, and 6 months post-operatively, pain medication use, days before return to work, duration of occupational therapy, as well as POSAS scores will be obtained and photos will be taken.

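### Pre-operative analgesic use and work status are not specified as data items, yet post-operative pain medication use and days to return to work are compared by unadjusted t-tests

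*Combined protocol and SAP*

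**What the plan says.** **Before surgery.** At enrolment (Section 6.1.1) the subject is seen by the Investigator, "who will then collect and record the subject's demographic information and medical history". At the pre-operative visit (Section 6.1.2), after eligibility screening, "medical history will be collected, a physical exam will be performed and medical photography will be obtained, as is the standard of care". Section 4.4 adds that enrolled patients "will proceed with baseline assessments once study consents have been signed and the patient has been enrolled in the study", but does not list those assessments. The synopsis refers to Section 1.2 for the visit schedule, and that schema is not shown in the available text.

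**After surgery.** Section 6.1.3 states that at 1 week, 1 month and 6 months "pain medication use, days before return to work, duration of occupational therapy, as well as POSAS scores will be obtained". Section 4.3 likewise places these measures at the post-operative visits. Section 11.1.1 has concomitant medications updated at post-baseline visits as part of adverse event questioning.

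**Analysis.** Section 9.3 hypothesises an earlier return to work and less pain medication in the endoscopic arm. Section 9.3.2 summarises both outcomes descriptively. Section 9.5 tests both with 2-sample t-tests and names no covariate. Section 9.2 says of all exploratory variables that nothing is to be derived from the reported values "except for the calculation of change from baseline, or change from prior time-points".

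None of the visible sections names pre-operative analgesic use or work status as a data item, covariate, stratum or exclusion. No rule says how days to return to work is scored for someone who was not working.

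**The concern.** Two secondary outcomes with directional hypotheses depend on the patient's state before the operation.

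- **Pain medication use.** Section 2.2 says that initial "nonsurgical management includes: non-steroidal anti-inflammatory drugs, activity modification, splinting, and corticosteroid injections". Some patients may therefore reach surgery already taking analgesics, and what they take afterwards is partly a continuation. Without the earlier value, the analysis cannot separate the two.
- **Days to return to work.** The entry criteria admit any adult over 18 and say nothing about employment. A subject who is not employed has no return date. For a subject already on leave because of the finger, the count continues an absence that began before surgery. Unless work status is recorded, neither can be told apart from a subject kept off work by the operation.

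With 12 patients per arm, a few such subjects can move an arm mean visibly, and a reader of the results could not judge whether that happened. Pre-operative status is also hard to reconstruct later.

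**Working it through.** **1. The plan's own figure.** Section 9.6 gives a difference of 10, SD 8, two-sided 5%, power 80% and 1:1 allocation. The standardised difference is 10/8 = 1.25. The t-based two-sample calculation gives 11.09 per arm, rounded up to 12 (power 79.6% at 11 and 83.3% at 12). The stated 12 per arm reproduces and is not in dispute. It is the input for the steps below.

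**2. Chance imbalance in a yes/no pre-operative state.** Let X and Y, each Bin(12, q), be the numbers in the two arms with the state (analgesic use, or not working). The documents give no prevalence, so q is an assumption and is shown as a range. Fair randomisation is also assumed. A gap of 3 of 12 is 25 percentage points.

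| q | P(gap of 3 or more) | P(gap of 4 or more) |
|---|---|---|
| 0.1 | 8.4% | 1.8% |
| 0.2 | 19.7% | 7.1% |
| 0.3 | 26.3% | 11.6% |
| 0.5 | 30.7% | 15.2% |

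The table is symmetric about 0.5, so q = 0.7 gives the same values as q = 0.3.

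**3. Continuous pre-operative value.** The standard error of the arm-mean difference is sqrt(2/12) = 0.41 SD. The probability of a gap of at least 0.5 SD is 2 × (1 − Φ(0.5/0.408)) = 22%.

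**4. What the imbalance does to the comparison.** With baseline-outcome correlation r (assumed), a baseline gap of 0.5 SD shifts the unadjusted difference by 0.5r SD. Adjustment for baseline reduces the residual variance to 1 − r².

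| r | Shift at a 0.5 SD gap | Residual variance after adjustment |
|---|---|---|
| 0.3 | 0.15 SD | 91% |
| 0.5 | 0.25 SD | 75% |
| 0.7 | 0.35 SD | 51% |

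**5. What it does not do.** In a simulation of 12 v 12 under random assignment, an unadjusted factor present in 50% of patients shifted the outcome by 0, 1 or 2 SD. The t-test's false-positive rates were 5.0%, 5.1% and 4.9%. The test already allows for chance imbalance.

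**6. Cost of restricting return to work to workers.** At 12 per arm, the difference detectable with 80% power is 1.20 SD. If 60% were working (0.6 × 12 = 7.2, taken as 7 per arm), it is 1.63 SD. At 50% (6 per arm), it is 1.80 SD. The working proportion is an assumption.

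**The case against.** The strongest case on the other side has four parts.

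**The information may be collected anyway.** Medical history is taken at enrolment and before surgery and reviewed at each follow-up visit. Section 4.4 plans baseline assessments, and the Section 1.2 schema cannot be seen. A reader might infer that no pre-operative record exists at all, and the documents do not support that. What stands is narrower: the visible text does not require these two items, and no analysis uses them.

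**Section 9.2 does not plan a change-from-baseline analysis.** A reader might infer that the plan commits to an analysis it cannot run. The sentence only permits the derivation, is worded for exploratory variables, and also allows change from prior time points, which can be calculated. No analysis in 9.3 or 9.5 depends on change from baseline. The scope is still unclear: the section heading names primary and secondary outcomes, while the only measure listed as exploratory in 8.1.3 is operative time, which has no baseline. That calls for a wording correction only.

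**Chance imbalance does not manufacture findings.** A reader might take the imbalance probabilities as the rate of spurious effects. Under random assignment they are not, as step 5 shows. This stands, and the loss is in precision and interpretability. The qualification is that randomisation is mentioned in only one inclusion criterion (Section 5.3) and no allocation procedure is described.

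**The extent of prior use is unknown.** Section 2.2 describes usual management of trigger finger, not the enrolled patients, and prior conservative treatment is not an entry criterion. At 10% prevalence the imbalance probability falls to 8.4%. This also stands. It bears on the analgesic comparison, but not on the lack of a return-to-work definition for subjects who were not working.

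**Conclusion.** The point holds as a modest one. The visible sections specify no pre-operative analgesic or work-status item, while Section 9.5 compares the corresponding post-operative outcomes without adjustment. Days to return to work is undefined for subjects not working before surgery; that conclusion rests on the text and on no assumed figure.

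The size of the analgesic problem does rest on assumptions. For prevalence of 10% to 50%, the arms differ by 3 or more of 12 patients with probability 8% to 31%. For correlations of 0.3 to 0.7, adjustment would remove 9% to 49% of the residual variance (100% minus the 91% to 51% in step 4). If allocation is not random, the differences need not be limited to chance, and the documents give no means of bounding them.

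Priority is limited because both outcomes are secondary, their main summary is descriptive, and the t-tests are labelled exploratory. The change is worth making because it is cheap and the data are hard to recover afterwards.

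**What to change.** - **Section 6.1.2:** add two items at the pre-operative visit: current analgesic use, and work status (working / on leave because of the finger / not employed). Record analgesic use in the same unit and recall period as the post-operative measure. The plan does not yet define either, so define them for both.
- **Section 4.4:** list what the baseline assessments are, consistent with the Section 1.2 schema.
- **Section 9.3.2:** report both items by arm.
- **Section 9.5:** compare post-operative analgesic use adjusted for the pre-operative value. Analyse days to return to work among subjects working before surgery, and give the number in each arm.
- **Section 9.2 (minor wording):** state which variables the sentence covers and limit change from baseline to those with a pre-operative value. POSAS has no scar to score before surgery, so it can use only change from prior post-operative time points.

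**Cost.** Two questions at an existing visit and some analysis wording, with no added patients or visits. The downside is fewer subjects in the return-to-work comparison, by a number that cannot be known in advance. Step 6 of the working shows the loss of sensitivity if only half to 60% were working.

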#### 9.2.1 PRIMARY OUTCOME MEASURES

Primary outcome measures include scarring based on Patient and Observer Scar Assessment Scale (POSAS) scores administered 1 week, 1 month, and 6 months post-operatively between patients treated with endoscopic versus open surgical release of the A1 pulley.

#### 9.2.2 SECONDARY OUTCOME MEASURES

Secondary outcome measures include pain medication use, overall patient satisfaction (score 1 to 10), days to return to work, and duration of post-operative occupational therapy as well as complication and recurrence rates after endoscopic versus open surgical treatment. Complications will include injury to tendons, nerves, and digital vessels noted during or after surgical treatment, as well as surgical site dehiscence and surgical site infections requiring antibiotics. Recurrence will be defined as triggering, confirmed on physical exam by treating physician, at any time point post-operatively.

#### 9.2.3 EXPLORATORY MEASURES

Operative time will be obtained from the operative record within the patient's electronic medical chart, as recorded by operative staff.

### 9.3 HYPOTHESIS AND METHODS OF ANALYSIS

We hypothesize that patients treated with the retrograde endoscopic approach will have improved scarring compared to patients treated with the open approach, based on POSAS scores obtained at 1 week, 1 month, and 6 months post-operatively. We also hypothesize that the patients in the endoscopic treatment arm will have a faster recovery (return to work sooner with fewer days of occupational therapy), have higher overall satisfaction (scale 1 to 10) and use less pain medication. We anticipate that the two treatments will not differ significantly in complication or recurrence rate.

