### 5 STUDY POPULATION CHARACTERISTICS

### 5.1 NUMBER OF SUBJECTS

Consecutive patients presenting with trigger finger interested in surgical release of the A1 pulley will undergo endoscopic versus open surgical release of the A1 pulley. A total of 12 subjects are to be enrolled for each treatment arm. Additional subjects may be enrolled, as needed to achieve 12 patients in each treatment arm, in the event of patient death or withdrawal from the study.

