#### 9.3.2 SECONDARY OUTCOME MEASURE ANALYSIS

Secondary outcome measures of pain medication use, overall satisfaction (scale 1 to 10), days to return to work, days of occupational therapy, complication rate, and recurrence rate will be analyzed using descriptive statistics, including n, mean, standard deviation, median, minimum, maximum, and skewness.

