## 9.5 EXPLORATORY ANALYSES

POSAS scores at 1 week, 1 month, and 6 months post-operatively will be analyzed between patients treated with endoscopic versus open release using 2-sample t-tests. Differences in pain medication use, days before return to work, duration of OT, operative time, overall satisfaction, complication and recurrence rates between patients treated with endoscopic versus open surgical release of the A1 pulley will be tested for significance using 2-sample t-tests. Additional analyses of possible relationships between outcomes may also be performed using appropriate inferential tests.

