## 9.6 SAMPLE SIZE CALCULATION

Total POSAS scores range from 12 to 120. Though the POSAS has not been used to assess scarring after trigger finger release, the tool is validated with high internal consistency and reliability.

The trial will be powered to detect a difference in POSAS score of 10, deemed to be clinically significant by the investigators. The POSAS standard deviations in studies previously published on carpal tunnel release and carotid endarterectomies ranges from 1.0 to 11.0. To detect a mean difference in POSAS score of 10 points (SD = 8) with a two-sided significance level of 5% and power of 80% with equal allocation to two arms would require 12 patients in each arm of the trial. Additional subjects may be enrolled, as needed to achieve 12 patients in each treatment arm, in the event of patient death or withdrawal from the study.

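### The plan expects no significant difference in complication and recurrence rates and tests for one, but with 12 per arm and no margin or interval, a non-significant result says little about similarity

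*Combined protocol and SAP*

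**What the plan says.** Section 9.3 (Hypothesis and Methods of Analysis) lists directional hypotheses for scarring, recovery, satisfaction and pain medication. It closes with "We anticipate that the two treatments will not differ significantly in complication or recurrence rate". The same sentence stands in the synopsis (Section 1.1, Statistical Methods).

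These rates are analysed in two places:

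- Section 9.3.2: "complication rate, and recurrence rate will be analyzed using descriptive statistics". The summaries listed there are n, mean, standard deviation, median, minimum, maximum and skewness.
- Section 9.5, as an exploratory analysis: "complication and recurrence rates between patients treated with endoscopic versus open surgical release of the A1 pulley will be tested for significance", by two-sample t-test.

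The sample size in Section 9.6 concerns another outcome: "To detect a mean difference in POSAS score of 10 points (SD = 8"), "with a two-sided significance level of 5% and power of 80"%, gives 12 per arm. Section 5.1 repeats that number. No section gives an expected complication or recurrence rate, a non-inferiority or equivalence margin, a power figure for these rates, or a confidence interval for their difference.

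**The concern.** Taken together, Sections 9.3 and 9.5 make a non-significant p-value the expected finding for complications and recurrence. With two small arms and infrequent events, that finding is likely whether or not the rates are similar, so it barely separates the two cases. The only other planned output is a set of summaries without an interval, so a reader would not see how large an excess the data leave open.

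This matters because Section 8.1.2 counts tendon, nerve and digital-vessel injury among the complications, and the endoscopic arm divides the pulley with a blade on an advancing instrument (Section 6.3). Recurrence bears on effectiveness as well as safety, and the same arithmetic applies to it. A short statement that the rates did not differ significantly could reassure later users more than 24 patients can justify.

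**Working it through.** **Inputs from the documents.** 12 per arm and equal allocation (Sections 5.1, 9.6); two-sample t-test (9.5); POSAS difference 10 and SD 8 (9.6). The two-sided 5% level is stated only for POSAS and is assumed here for the rates.

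**Other assumptions.** Each outcome is one yes/no result per subject, and all 12 per arm are analysed. True event rates are not in the documents, so a range is used.

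**1. The plan's own figure.** Normal approximation: n = 2 × (1.960 + 0.842)² × 8² / 10² = 10.05, so 11 per arm. The t-test solution is 11.09, so 12 per arm, with 83.3% power at 12. The stated sample size reproduces. It says nothing about event rates.

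**2. What it takes to reach significance.** Suppose the open arm has 0/12 events and the endoscopic arm a/12.

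- t-test, a = 3: endoscopic variance = 12 × 0.25 × 0.75 / 11 = 0.2045; pooled variance 0.1023; SE = √(0.1023 × 2/12) = 0.1306; t = 0.25/0.1306 = 1.915 on 22 df; p = 0.069.
- t-test, a = 4: t = 0.3333/0.1421 = 2.345; p = 0.028.
- Fisher's test, p = 2 × C(12,a)/C(24,a): 0.217 for a = 3, 0.093 for a = 4, 0.037 for a = 5.

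So a 25% versus 0% split is non-significant by either test. With 1/12 open-arm events, significance needs 6/12 (t-test) or 7/12 (Fisher).

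**3. How often the result is non-significant.** All 13 × 13 outcomes were enumerated:

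P(non-significant) = Σ Bin(a; 12, p_E) × Bin(b; 12, p_O), summed over pairs (a, b) with p ≥ 0.05.

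| Assumed open rate | Assumed endoscopic rate | Ratio | t-test | Fisher |
|---|---|---|---|---|
| 1% | 5% | 5 | 99.8% | 99.98% |
| 2% | 10% | 5 | 98.0% | 99.7% |
| 3% | 15% | 5 | 93.5% | 98.3% |
| 5% | 15% | 3 | 94.8% | 98.7% |
| 5% | 25% | 5 | 79.0% | 91.0% |
| 10% | 30% | 3 | 80.2% | 90.5% |
| 10% | 50% | 5 | 40.0% | 57.5% |

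The Welch and pooled t-tests agree in every row. Fisher's test is non-significant more often than the t-test throughout, so changing the test alone does not remove the problem.

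**4. What remains open when nothing is seen.** For 0/12, the Wilson upper limit is z²/(n + z²) = 3.84/15.84 = 24.2%. The Newcombe interval for 0/12 versus 0/12 is 0 ± √(0² + 0.242²), about -24 to +24 points. For 3/12 versus 0/12 it is about -4 to +53 points.

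**5. What a similarity claim would need.** Illustration only: n = (1.960 + 0.842)² × 2p(1 - p)/margin², at one-sided 2.5%, 80% power and equal true rates of 5%. A 10-point margin needs 7.85 × 0.095 / 0.01 = 74.6, so 75 per arm. A 5-point margin needs 299 per arm.

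**The case against.** The strongest reply is that the plan never commits the error. No section says that non-significance will be reported as similar or equivalent safety. Section 9.3 hypothesizes about the other outcomes and only anticipates here. Section 9 calls all the analyses descriptive, the synopsis calls 24 patients enough for descriptive summaries and exploratory analyses, and the tests appear only under Exploratory Analyses. The safety analysis proper (Section 9.3.4) tabulates adverse events with no test. All of that stands.

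A reader might also infer that a non-significant result is close to certain even if the endoscopic technique is several times more harmful. The documents do not support that as a general statement, because they give no event rate for either arm. At 10% versus 50% the planned t-test misses the excess in only 40% of trials.

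Finally, dropping the test could lose a signal of gross harm, since 4/12 versus 0/12 gives p = 0.028. This weighs against simply deleting the test. It does not weigh against an interval: the Newcombe interval for 4/12 versus 0/12 runs from about +2 to +61 points and excludes zero.

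What the reply does not meet is that the sentence stands in the hypothesis section, in the language of significance, beside a planned significance test and with no interval. Calling the test exploratory does not make its non-significance informative about similarity.

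**Conclusion.** The concern holds in a limited form. The only inferential output planned for complication and recurrence rates is a p-value, and the stated expectation is that it will be non-significant. With 12 per arm, that result could not support a conclusion of similar rates.

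The size depends on assumed rates. Non-significance occurs in about 93% or more of trials for a fivefold excess over an open-arm rate of 1-3%, or a threefold excess over 5%. It is clearly less likely at higher rates. The interval of about ±24 points at zero events in both arms needs no assumed rate.

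A reader might go further and conclude that the plan will declare the techniques equally safe. The text does not say so. The point is a weakness in the stated criterion, and no wrong conclusion has yet been drawn. The POSAS sample size arithmetic is not in question. This should be fixed, but it is not a must-fix: both rates are secondary outcomes, and no primary result, stopping rule or enrolment number rests on the sentence.

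**What to change.** 1. In Section 9.3 and the synopsis, replace the sentence with: *Complication and recurrence rates will be described by arm; the trial is not designed to show that they are similar, and a non-significant difference will not be interpreted as similarity.*
2. In Sections 9.3.2 and 9.5, for these two outcomes, report event counts by arm and the risk difference (endoscopic minus open) with a two-sided 95% Newcombe (score) interval, in place of the t-test.
3. If a p-value is kept, label it exploratory and obtain it by Fisher's exact test.

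The cost is wording in four places and a weaker safety statement than the sponsor may have hoped for. No extra patients, visits or data are needed.
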